# 4.5 Exploratory Outcomes, Phase II

Tests planned for Phase II are shown in **Table 7** and **Table 8**. With regard to the analyses with outcome variable "Treatment Success", Treatment Success will be defined as follows:

#### Treatment Success from Original Injection

- (1) No additional injections
- (2) No cross-over or study exit for other invasive treatment
- (3) Clinically meaningful improvement in WOMAC Pain score (>20% from baseline)

#### Treatment Success from Original Treatment Assignment

- (1) No cross-over or study exit for other invasive treatment
- (2) Clinically meaningful improvement in WOMAC Pain score (>20% from baseline)

The items in **Table 7** will be analyzed according to the original treatment assignment (APS or HA). The items in **Table 8** will use Treatment / Crossover group as the predictor variable: (1) randomized to APS and not crossed over to HA, (2) randomized to APS and crossed over to HA, (3) randomized to HA and crossed over to APS and (4) randomized to HA and not crossed over to APS. For all tests where the Treatment / Crossover Group is the predictor variable, patients progressing to other invasive treatment for their OA will be included as a Non-Responder (where OMERACT-OARSI responder is the outcome variable) or using the most recently collected outcome score (where pain, function or EQ-5D is the outcome variable).

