	μ_{HA} is the mean change in WOMAC Pain from baseline to 12
	months for HA group.
Secondary Endpoints	The subjects showing a minimum clinically important difference
	(MCID) in the WOMAC Function subscale
	The subjects showing a minimum clinically important difference
	(MCID) in the WOMAC Pain subscale
	Change in function as measured by the WOMAC function scale
	(baseline to 12 months)
	Percentage of subjects achieving clinical success as defined by
	OMERACT-OARSI Responder Criteria (1) and including
	restricted and rescue medication usage
	Change in pain as measured by the WOMAC pain scale
	(baseline to 12 months) in KL-II subgroup
	Change in function as measured by the WOMAC function scale
	(baseline to 12 months) in KL-II subgroup
	• The effects of rescue and restricted medication on changes in
	WOMAC pain (baseline to 12 months)
	Change in pain as measured by the NRS pain scale (baseline
	to 12 months)
	Change in WOMAC LK 3.1 Pain subscale over time
Exploratory	The following exploratory endpoints will be assessed at all post-
Endpoints:	injection time points:
	Change in pain as measured by NRS pain scale
	Percentage of subjects achieving clinical success as defined by
	OMERACT-OARSI Responder Criteria (1)
	• Change in WOMAC LK 3.1 pain (excluding 12-month time
	point), function and stiffness subscale scores
	Change in overall WOMAC LK 3.1 score
	Change in quality of life and global assessment as measured
	by the EQ-5D-3L and EQ-VAS
	• The effects of rescue and restricted medication on changes in
	WOMAC pain (baseline to 12 months)

The following secondary endpoints will be assessed until the 24-
month follow-up:
 Joint Space Narrowing (JSN)
 Correlation of JSN to change in NRS pain score
 Relationship between JSN and OMERACT-OARSI status
Change in K-L grade
The following endpoints will be assessed at all long-term follow-up time points (months 12 - 60):
 Percentage of patients achieving treatment success from initial
injection (i.e. patients who have not received additional
injection, cross-over, or study exit for other invasive treatment
and have clinically meaningful improvement in WOMAC Pain
score ⁶)
 Percentage of patients achieving treatment success from originally assigned treatment (i.e. patients who have not crossed over or exited the study due to dissatisfaction with symptom relief and have clinically meaningful improvement in WOMAC Pain score)
• Percentage of patients achieving success in each treatment

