arm (i.e. patients with clinically meaningful improvement in
WOMAC Pain score, inclusive of originally assigned and cross-
over patients)
 Average number of cumulative interventions per patient
• Time from the initial injection (nSTRIDE APS or HA) to
subsequent injection(s), cross-over, or study exit for other
invasive treatment
 Resource utilization for index knee OA.

⁶ Clinically meaningful improvement is considered to be an improvement of at least 20% from baseline

	The following endpoint will be assessed annually in the long-term
	follow-up phase for patients that have crossed over:
	Percentage of patients preferring each treatment due to:
	1. Greater pain relief
	2. Longer lasting pain relief
	3. Greater improvement in function
	4. Longer lasting improvement in function
	5. Fewer post-injection side effects
Safety Endpoints	Occurrence of all AEs up to 12 month time-point and
	occurrence of AEs of interest across all post-operative time
	points

This Clinical Investigation Plan is written in accordance with ISO14155:2011 "Clinical Investigation of medical devices for human subjects – Good clinical practice" (40). The Adverse Events sections is written in accordance with the ISO14155:2020 "Clinical Investigation of medical devices for human subjects – Good clinical practice" (41).

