#### Per Protocol (PP)

The PP population includes all subjects from the mITT population who do not have major protocol deviations that impact patient safety or the scientific validity of the study outcomes, or the potential to do so. Analyses which use the PP population will use all available data on these subjects, with no imputation of missing data. This is the population that will be used in the analysis of secondary and exploratory efficacy endpoints, and as a sensitivity analysis of the primary endpoint.

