# 6.3 Missing Data and Sensitivity Analyses

# 6.3.1 Imputation of Missing Data in the Primary Analysis

The primary analysis will be performed on the ITT population. In the primary analysis, missing WOMAC Pain scores for subjects who are withdrawn due to reasons related to the index knee OA ("non-responders") will be considered Missing Not At Random (MNAR), and the subjects' baseline score will be carried forward in the analysis of WOMAC Pain. Scores missing for all other reasons will be considered Missing At Random and will be imputed using a Multiple Imputation method, which will replace each missing value with a set of plausible values that represent the variability around the choice of which value to impute. The monotone regression method will be used [22], and will include variables from **Table 1** (i.e. gender, age, BMI, race, and preop WOMAC Pain) as well as treatment group. As suggested in Bodner and White et al [23, 24], the number of imputations will reflect the percentage of incomplete cases. Approximately 15% attrition is estimated in the sample size calculation and thus approximately fifteen imputed datasets will be incorporated, and a seed of 20190516 will be used in generating the random numbers.

No imputation of missing values is planned for secondary or exploratory outcome variables.

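### For one exploratory Phase II endpoint, success from the originally assigned treatment, the SAP and protocol count different study exits as failure, and their 20% pain thresholds also differ at exact ties

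*SAP*

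**What the plan says.** The protocol synopsis (Exploratory Endpoints, long-term list) separates two endpoints by their exit rule. Success from the initial injection excludes subjects with a further "injection, cross-over, or study exit for other invasive treatment". Success from the originally assigned treatment is limited to "patients who have not crossed over or exited the study due to dissatisfaction with symptom relief" who also improve meaningfully on WOMAC pain. Footnote 6 sets the bar: "Clinically meaningful improvement is considered to be an improvement of at least 20% from baseline".

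SAP section 4.5 uses the invasive-treatment rule for both endpoints. Under Treatment Success from Original Treatment Assignment the exit condition is "No cross-over or study exit for other invasive treatment". The pain condition under both SAP definitions is "Clinically meaningful improvement in WOMAC Pain score (>20% from baseline".

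On missing data, section 6.3.1 states "No imputation of missing values is planned for secondary or exploratory outcome variables", and the Per Protocol paragraph of section 6 states "Analyses which use the PP population will use all available data on these subjects, with no imputation of missing data". Section 4.5 has one rule for Phase II leavers: "patients progressing to other invasive treatment for their OA will be included as a Non-Responder" when the outcome is the OMERACT-OARSI classification, or with their latest score when it is pain, function or EQ-5D. That rule is confined to tests with Treatment / Crossover Group as predictor (Table 8). The success endpoints are in Table 7, which is analysed by original assignment.

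**The concern.** Two governing documents define one named endpoint differently, so the reported rate depends on which is followed. The subjects at issue leave because relief was inadequate, do not cross over, and do not leave for invasive treatment. The protocol calls them failures. Under the SAP they satisfy the exit condition, and at visits after they leave they have no WOMAC score with which to judge the pain condition. The SAP does not say how they are counted. If they are set aside as missing, the arm with more such exits loses more of its failures from the denominator, and a real difference between arms in dissatisfaction could disappear from the comparison.

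The SAP treats the comparable situation differently for the primary endpoint. In section 6.3.1, subjects withdrawn for reasons related to index-knee OA are non-responders, with the baseline score carried forward. No equivalent is given for this endpoint.

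**Working it through.** The plan states no figure that depends on these definitions, so there is none to reproduce. The check sets the texts side by side, then sizes the effect under assumptions.

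**Exit rule, success from the originally assigned treatment**

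| Subject | Protocol | SAP 4.5 |
|---|---|---|
| Crosses over | failure | failure |
| Leaves dissatisfied, for invasive treatment | failure | failure |
| Leaves dissatisfied, no invasive treatment | failure | not a defined failure; no later score |
| Leaves for invasive treatment, not dissatisfied | not named | failure |

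The third and fourth rows differ, in opposite directions. For success from the initial injection, the exit rules agree.

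**Size of the third-row difference**

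Inputs: n = 123 per group (SAP 6.1). Assumed, because neither document gives them: success proportion s = 60% among subjects who stay, and a proportion e = 5% to 25% who leave dissatisfied without invasive treatment. Let L be the number of leavers (123e, rounded) and S the number of successes (0.6 × (123 − L), rounded).

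- Protocol rule: S / 123.
- SAP, if leavers are treated as missing: S / (123 − L).

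| e | L | S | Protocol | SAP, leavers left out | Gap (points) |
|---|---|---|---|---|---|
| 5% | 6 | 70 | 70/123 = 56.9% | 70/117 = 59.8% | 2.9 |
| 10% | 12 | 67 | 67/123 = 54.5% | 67/111 = 60.4% | 5.9 |
| 15% | 18 | 63 | 63/123 = 51.2% | 63/105 = 60.0% | 8.8 |
| 20% | 25 | 59 | 59/123 = 48.0% | 59/98 = 60.2% | 12.2 |
| 25% | 31 | 55 | 55/123 = 44.7% | 55/92 = 59.8% | 15.1 |

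Ignoring rounding, the gap is s − s(1 − e) = s × e: 0.60 × 0.05 = 3 points up to 0.60 × 0.25 = 15 points. With no such leavers it is zero.

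For the comparison between arms, take 20% leavers in one arm and 5% in the other, with 60% success among stayers in both. The protocol rule gives 56.9% − 48.0% = 8.9 points. Leaving them out gives 60.2% against 59.8%, a difference of 0.4 points that is only rounding.

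**Threshold**

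WOMAC pain is the sum of five items scored 0 to 4, so totals are whole numbers when all items are answered. Eligible baselines are 9 to 19. An exact 20% improvement is a whole number only when the baseline is a multiple of 5:

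- Baseline 10: 20% is 2 points. At least 20% needs 2; more than 20% needs 3.
- Baseline 15: 20% is 3 points. At least 20% needs 3; more than 20% needs 4.
- At the other nine eligible baselines the two rules need the same improvement.

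**The case against.** The strongest objection is that the SAP nowhere says a leaver without a score drops out of the denominator. Success is a composite, Table 7 reports a percentage of patients, and a subject with no score has not shown the required improvement. Counting that subject as not a success needs no imputed value. This stands as a possible reading. A reader might infer that the SAP prescribes exclusion; it does not. Exclusion is the likelier outcome of available-data analysis without imputation, but the actual defect is that the SAP is silent.

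A reader might also infer a one-way bias in favour of the worse arm. The documents do not support that. The effect depends on the missing-data reading. Invasive-treatment exits without dissatisfaction diverge in the other direction. The stricter SAP threshold can only lower its success count.

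The affected group may also be small. The protocol offers further injections of the assigned treatment or a cross-over, and subjects who seek other invasive treatment instead leave the study. Cross-over and invasive-treatment exit already fail under the SAP. No document gives a rate for the remainder, so the lower end of the range, or less, is possible.

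On the threshold, the greater-than sign could be an underlined symbol that lost its line in the PDF text. Against that, the greater-or-equal sign is intact in the responder definitions of SAP section 4.3. The point is uncertain and should be checked against the signed SAP.

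**Conclusion.** The two documents conflict on the exit rule for success from the originally assigned treatment and should be reconciled. Under the SAP, a dissatisfied leaver without invasive treatment is not a defined failure and may be treated as missing. If so, the success rate lies about 3 to 15 percentage points above the protocol's rate, given the assumed 60% success among stayers and 5% to 25% such leavers. These inputs are illustrative and come from neither document.

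The threshold difference is minor: one point at 2 of the 11 eligible baselines. It is the only difference for success from the initial injection, so it would be wrong to infer that the exit problem runs through every treatment-success endpoint.

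The endpoint is exploratory and tested without multiplicity adjustment (SAP section 1), and nothing ranks it above the other Table 7 outcomes. The primary and secondary tests, alpha and sample size do not depend on it. This is a low-severity correction, worth making because the reported rate would otherwise depend on an unstated choice.

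**What to change.** In SAP section 4.5, under Treatment Success from Original Treatment Assignment:

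- replace the exit condition with the protocol's, so that leaving because of dissatisfaction with relief counts as failure;
- state that such leavers stay in the denominator as failures at every later visit, whether or not a WOMAC score exists.

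Under both treatment-success definitions in section 4.5, write the pain threshold as at least 20%, to match protocol footnote 6.

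This costs SAP wording only. It relies on the reason for exit being recorded, which the protocol definition already presupposes. If exits for other invasive treatment are also meant to count as failures for this endpoint, that combined rule is in neither document, and the protocol wording would have to be amended to match.

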Secondary objectives of this study include determining whether nSTRIDE APS is superior to HA in improving WOMAC LK 3.1 function at 12 months (as evaluated using the percentage of subjects showing at least the minimal clinically important difference (MCID)), and WOMAC LK 3.1 pain at 12 months (as evaluated using the percentage of subjects showing at least the minimal clinically important difference (MCID)), OMERACT-OARSI responder rates at 12 months, analyzing WOMAC pain and function in only the KL-II Subgroup at 12 months, evaluating superiority of APS over HA in improving Numeric Rating Scale (NRS) pain at 12 months, assessment of the changes in WOMAC Pain scores over time (baseline through 12 months), and evaluation of the usage of rescue medication within 12 months. These will be tested in a fixed sequential order pending the rejection of the primary null hypothesis.

Exploratory objectives of this study include determining whether APS is superior to HA with regards to improvement in mean EQ-5D outcomes (12 months minus baseline) and repeated measures of WOMAC Function, WOMAC stiffness, and total WOMAC score. In addition, changes in joint morphology (determined with X-ray images) will be evaluated. Subgroup analyses will be conducted to investigate whether the treatment effect varies depending on subjects' initial pain and baseline information. Analysis of exploratory endpoints will be done using alpha=0.05 with no adjustment for multiple comparisons.

A long-term follow-up phase will examine the superiority of nSTRIDE APS in the duration of the treatment effect, injection frequency, patient preferences, healthcare resource utilization, and associated costs. These endpoints will be treated as exploratory endpoints and analyses will be conducted using alpha = 0.05 with no adjustment for multiple comparisons.

Finally, the safety profile of nSTRIDE APS will be compared to HA by comparing adverse events and rates between treatment groups.

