### 1.3 Randomization

Subjects will be randomized to either the APS or HA treatment group on a 1:1 basis. The subjects and investigators will both remain blinded throughout Phase I of the study. Assignment to treatment groups will be stratified by site and will use random block sizes. Specifically, designated unblinded personnel at each site will provide the masked syringe to the injecting health care provider. To protect the double-blind, the treating health care professional and evaluating health care professional will be different individuals. Assignment will not be revealed until after the blood has been drawn for nSTRIDE APS Kit processing.

The randomization plan will be produced using SAS v 9.4 or similar software. Balanced randomization with random block sizes (1:1, APS: HA) will be implemented. In the event that, post-randomization, no study treatment was given, randomization will not be reassigned; however, this case will not count toward the overall sample size. Randomization will continue with the next case enrolled until the minimum sample size is reached in both treatment groups. Randomization will be stratified by site, and each site will receive separate randomization plans using random predetermined block sizes that will remain undisclosed to the sites. The randomization file will be uploaded into the electronic data capture (EDC) system. Once the subject is enrolled into the EDC and has been identified as eligible for randomization, the randomization allocation will be visible within the EDC and viewable only by the unblinded research associate. The subject will be treated according to the contents of the displayed randomization allocation.

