# Table 8 - Planned Phase II Statistical Analysis – Treatment/Crossover Group

Predictor Variable	Outcome Variable(s)	Statistic	Expected Outcome
Treatment / Crossover Group	Progression to other invasive OA treatment	Chi-Square	Trend APS Superior

Treatment / Crossover Group	OMERACT-ORSI Responder / Non- Responder	Chi-Square	Trend APS Superior
Treatment / Crossover Group	WOMAC Pain, 6 Mo Intervals	One-Way Anova	Trend APS Superior
Treatment / Crossover Group	WOMAC Function, 6 Mo Intervals	One-Way Anova	Trend APS Superior
Treatment / Crossover Group	NRS Pain, 6 Mo Intervals	One-Way Anova	Trend APS Superior
Treatment / Crossover Group	EQ-5D Global Assessment 6 Mo Intervals	One-Way Anova	Trend APS Superior
Treatment / Cross Over Group	Patient Preference	Chi-Square	Trend APS Superior
Treatment / Cross Over Group	WOMAC Pain Δ: Baseline-12M	Summary Statistics and ANCOVA Model*	Trend APS Superior
Treatment / Cross Over Group	WOMAC Pain ∆: Baseline-6M	Summary Statistics and ANCOVA Model*	Trend APS Superior
Treatment / Cross Over Group	Percent of Subjects in each Treatment/Cross Over Category	Chi-Square	Trend APS Superior

\*Analysis of Covariance models will be used in order to determine if changes in WOMAC Pain score from Baseline to12 months (first model) or from 6 to 12 months (second model) differ according to what type of 2nd injection they chose to receive ( $\beta_3$ ), and whether this difference varies for APS and HA ( $\beta_2$  \*  $\beta_3$ ). The model will be as follows:

 $Y=\beta_0+\beta_1+\beta_2+\beta_3+\beta_2*\beta_3$ 

Where

 $\beta_0$ = Intercept

 $\beta_1$ = Baseline WOMAC Pain score

 $\beta_2$  = Treatment Group

 $\beta_3$ = 2nd Injection (None, Same, Crossover)

Y= Change in WOMAC Pain

In addition to these tests, results of the patient preference questionnaire will be tabulated by crossover group.

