# 6.3.2 Sensitivity Analyses

Scores for subjects who are withdrawn due to reasons related to the index knee OA are considered Missing Not At Random. In all of the ITT analyses described below, these subjects will be considered "non-responders", and the subjects' baseline score will be used in the analysis of WOMAC Pain.

The primary study analysis assumes that the all other missing data is Missing At Random (MAR).

In order to investigate the assumption that the missing data (excluding the non-responders who are withdrawn for reasons related to the index knee OA)

<sup>2 If data are severely non-normal based on a graphical review, then the predictive mean matching method will be used instead of the monotone regression method.

is MAR, sensitivity analysis of the primary study endpoint will be performed under assumption of other missing data mechanisms, as follows:

- 1. A complete case analysis on the ITT population (Missing Completely at Random (MCAR))
- 2. A complete case analysis on the Per Protocol population (Missing Completely at Random (MCAR))
- 3. A tipping point analysis on the ITT population, performed under the assumption that the data is not MAR or MCAR by searching for a tipping point that reverses the study conclusion. This analysis will examine the possibility that the distribution of missing responses will have a different expected value than that of the corresponding distribution of the observed responses. Thus, the analysis will generate multiple imputed data sets with a specified sequence of shift parameters that adjust the imputed values for observations in the treatment group (Missing Not At Random (MNAR)).

In the event the conclusion from one or more of the sensitivity analyses disagrees with the conclusion from the primary analysis, the sources of differences between them will be investigated and subjected to explicit discussion and interpretation.

Prior results indicate that the efficacy of APS and the saline control differs over time, but this difference is small until some point after the 6 month postinjection time point. Therefore, although carrying data forward from an earlier time is commonly applied as a sensitivity analysis, in this case it is likely to produce misleading results if applied to primary endpoints and so is not planned.

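### Phase II scores, responder status, QALYs and costs are compared only across self-selected crossover groups, so these outcomes have no planned randomised APS-versus-HA comparison

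*SAP*

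**What the plan says.** SAP section 1 sets the long-term objective as superiority. It states that Phase II "will examine the superiority of nSTRIDE APS in the duration of the treatment effect, injection frequency, patient preferences, healthcare resource utilization, and associated costs". Long-term endpoints are classed as exploratory. Exploratory endpoints are tested "using alpha=0.05 with no adjustment for multiple comparisons".

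Section 4.5 splits the Phase II analyses in two.

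- **Table 7** is analysed by original assignment. It covers election to cross over, three treatment-success rates that include a WOMAC Pain improvement above 20%, cumulative interventions, and time to next injection, crossover or exit for other invasive treatment.
- **Table 8** "will use Treatment / Crossover group as the predictor variable". The four groups are APS stayed, APS to HA, HA to APS and HA stayed. Its rows include "WOMAC Pain, 6 Mo Intervals", the matching rows for WOMAC Function, NRS pain and EQ-5D global assessment (all by one-way ANOVA), and chi-square tests of OMERACT-OARSI response and progression to other invasive treatment.

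Table 9 (section 4.6) uses the same four groups for QALYs, the EQ-5D index and every cost row. The expected outcome for all these rows is a trend in favour of APS. None of them is also listed by randomised arm.

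Section 1.2 makes crossover the subject's own choice, available in months 12 to 60 and once only. Table 7 expects more HA than APS subjects to make that choice.

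**The concern.** The only groups that randomisation makes comparable are the two original arms: "Subjects will be randomized to either the APS or HA treatment group on a 1:1 basis". The four Treatment/Crossover groups are formed later, by a choice that may depend on how the subject has fared. Table 7 itself treats that choice as an outcome affected by treatment, and Tables 8 and 9 then use it as the predictor. A difference between the groups can therefore come from treatment, from who chose to move, or from both, and the planned tests cannot separate these.

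The test form adds a second problem. The null hypothesis of a four-group one-way ANOVA or chi-square is that all four groups are equal. A rejection does not say which groups differ or in which direction, and the SAP specifies no APS-versus-HA contrast to follow it.

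At stake is what may be said after five years about APS against HA on scores, quality of life and cost. A significant Table 8 or 9 result could be read as long-term superiority when it reflects selection.

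**Working it through.** **1. The objective set against the tables.** Section 1 names five components.

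| Component | Listed comparison by randomised arm |
|---|---|
| Duration of effect | Yes: Table 7, time to next injection, crossover or exit |
| Injection frequency | Yes: Table 7, cumulative interventions |
| Patient preference | None; per the protocol synopsis it is assessed only in subjects who crossed over |
| Resource utilisation | None listed |
| Costs | None; Table 9 by crossover group only |

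Two of five have a randomised comparison. Preference cannot have a full one. Resource use and cost could, but do not.

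**2. Does the Table 8 ANCOVA fill the gap?** Its terms are baseline WOMAC Pain, treatment group, second injection (none, same, crossover) and the interaction of the last two. The treatment term is thus conditional on the second injection that the subject chose. It does not restore the randomised contrast.

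**3. Size of the selection effect (illustration).** The documents give no Phase II power, crossover rate or between-visit correlation, so there is no plan figure to reproduce.

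- From SAP section 6.1: 93 per arm and SD 4.06 for WOMAC Pain improvement.
- Assumed: identical treatments; correlation r between 12-month and later improvement of 0.3, 0.5 or 0.7; crossover probability h for subjects below the median 12-month improvement and l = 0.10 for the others, the same in both arms.
- 2,000 simulated trials per setting.

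The expected gap between APS stayed and HA to APS, from selection alone, can be checked by formula:

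gap = r × SD × √(2/π) × [(h − l)/(2 − h − l) + (h − l)/(h + l)]

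- h = 0.30: 0.798 × (0.2/1.6 + 0.2/0.4) = 0.798 × 0.625 = 0.499. With r = 0.3: 0.3 × 4.06 × 0.499 = 0.61.
- h = 0.50: 0.798 × (0.4/1.4 + 0.4/0.6) = 0.798 × 0.952 = 0.760. With r = 0.7: 0.7 × 4.06 × 0.760 = 2.16.

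| r | h | Four-group ANOVA rejects | By-arm t-test rejects | Simulated gap (points) |
|---|---|---|---|---|
| 0.3 | 0.30 | 9.3% | 4.4% | 0.63 |
| 0.3 | 0.50 | 19.1% | 5.4% | 0.89 |
| 0.5 | 0.30 | 16.5% | 4.9% | 0.99 |
| 0.5 | 0.50 | 49.4% | 5.2% | 1.55 |
| 0.7 | 0.30 | 31.5% | 4.0% | 1.40 |
| 0.7 | 0.50 | 83.4% | 4.5% | 2.15 |

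The simulated gaps agree with the formula. The mean by-arm difference stays near zero throughout. If crossover is unrelated to 12-month response (30% in everyone), or if r = 0, both tests reject in about 4% to 6% of trials.

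**The case against.** **Table 7 is a randomised long-term analysis.** This is correct. A reader who stops at "A long-term follow-up phase will examine the superiority of nSTRIDE APS in the duration of the treatment effect" might infer that the long-term question has no randomised comparison at all. The documents do not support that. Duration and injection frequency are tested by original assignment, and so is pain in dichotomised form. One Table 7 row, success inclusive of crossover patients, might be run as treated in practice, but the stated rule for the table is original assignment.

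**Mean scores are not among the five components.** True of SAP section 1. However, the protocol synopsis states an exploratory superiority objective for patient-reported pain, function, stiffness and quality of life, and lists score endpoints at all post-injection time points. A by-arm analysis of the later visits is therefore within the trial's stated aims.

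**Not every row is a one-way ANOVA, and a cost-effectiveness analysis is also planned.** Both stand. The chi-square rows and the repeated-measures or Friedman row for the EQ-5D index still use the self-selected groups, and section 4.6 does not say how the cost-effectiveness analysis will group subjects.

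**The direction of selection is unknown.** A reader might assume that stayers stay because they benefit. The benefit condition in section 1.2 attaches to further injections, and the non-crossover groups also hold subjects who took no second injection. Only the elective nature of the choice is established.

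**Carry-forward.** Under section 4.5, subjects who progress to other invasive treatment are analysed "using the most recently collected outcome score", while section 6.3.2 says of carrying data forward that "in this case it is likely to produce misleading results if applied to primary endpoints". A reader might see a contradiction. The reason given in 6.3.2 is specific to the primary endpoint: the difference between APS and saline is small until some point after 6 months. It does not transfer to Phase II.

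**Exploratory status.** It limits the severity. It does not make a p-value across self-selected groups interpretable as APS against HA.

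**Conclusion.** The concern holds for a defined set of outcomes: Phase II WOMAC Pain and Function, NRS pain and EQ-5D scores, OMERACT-OARSI response, progression to other invasive treatment as a separate outcome, QALYs and the Table 9 cost rows. For these the plan has no comparison that randomisation protects, and the omnibus tests cannot show that APS is better.

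Under the assumptions shown, selection alone raises the rejection rate of the four-group ANOVA to between 9% and 83%. These figures illustrate a mechanism and do not predict this trial's result, because the crossover rates and correlations are assumed. A reader might infer that the selection gap exceeds the 2.27 points used for sample size. It does not in this range, where the gap between APS stayed and HA to APS is 0.6 to 2.1 points.

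The change is cheap and worth making. The 12-month primary analysis is not touched.

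**What to change.** Add to SAP sections 4.5 and 4.6 an analysis by original randomised arm for the outcomes named above:

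- for the scores, for example a mixed model over the Phase II visits, with the arm difference and its confidence interval at each visit;
- for OMERACT-OARSI response, progression to other invasive treatment, QALYs and costs, a direct two-arm comparison.

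State that these analyses are the basis for any long-term APS-versus-HA statement, and label the crossover-group results descriptive. State also how scores are handled after exit for other invasive treatment, because the section 4.5 rule is written only for tests that use the crossover grouping.

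Leave out patient preference, the Baseline-12M and Baseline-6M rows, and the row counting subjects per crossover category. Reconcile the Table 9 medication-cost row marked Phase I with the statement in section 4.6 that cost data are not collected in that phase.

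The cost is SAP wording and a few tables, with no new data. The downside is dilution: once subjects cross over, the by-arm comparison estimates the effect of initial assignment followed by whatever subjects chose, which will tend to be smaller than any effect of staying on one treatment.
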